9.7. Exposure In Utero During Clinical Studies

The Sponsor must be notified of any subject who becomes pregnant while receiving, or within 3 months of discontinuing, the study drug. Sponsor must be notified of any male subject whose female partner becomes pregnant while the subject is receiving, or within 3 months of discontinuing, the study drug.

Although pregnancy is not technically an AE, all pregnancies must be followed to conclusion to determine their outcome. This information is important for both drug safety and public health concerns. It is the responsibility of the Investigator, or designee, to report any pregnancy in a female subject using the Exposure In Utero (EIU) Reporting form. Please contact your study monitor to receive the EIU Reporting Form upon learning of a pregnancy. The Investigator should make every effort to follow the subject until completion of the pregnancy and complete the EIU Reporting Form with complete pregnancy outcome information, including normal delivery and induced abortion. The adverse pregnancy outcome, either serious or non-serious, should be reported in accordance with study procedures. If the outcome of the pregnancy meets the criteria for immediate classification as a SAE (ie, post-partum complications, spontaneous or induced abortion, stillbirth, neonatal death, or congenital anomaly, including that in an aborted fetus), the Investigator should follow the procedures for reporting SAEs outlined in Section 9.5.

9.8. Clinical Laboratory Evaluations

For clinical laboratory parameters, the reference range of the institution that performs the measurements will be used.

Clinical laboratory results will be entered in the eCRF, including whether measurements were obtained, date of measurement, and results of measurements.

Standard clinical laboratory tests listed in [Table 9.1](#) should be performed per the Schedule of Events ([Table 6.1](#), [Table 6.2](#), and [Table 6.3](#)).

At Screening, creatinine clearance (mL/min) will be calculated using the Cockcroft-Gault equation (Section 17.1).

In addition, a serum pregnancy test (beta hCG) will be required for all female subjects of childbearing potential at Screening. Urine pregnancy tests will be performed throughout the remainder of the protocol per the Schedule of Events ([Table 6.1](#), [Table 6.2](#), and [Table 6.3](#)). A positive urine pregnancy test result must be confirmed immediately using a serum test.

Table 9.1: Clinical Laboratory Tests

Laboratory Tests	Parameters
Hematology	Red blood cell count, Hb, hematocrit, platelet count, white blood cell count, differential white blood cell count (neutrophils, lymphocytes, monocytes, eosinophils, basophils)
Chemistry	Total protein, albumin, ALP, ALT, AST, TBL, BUN, calcium, chloride, CK, serum creatinine, lipase, LDH, magnesium, potassium, sodium, FSH (if indicated), estradiol (if indicated), T3[FT3] ^a , TSH ^a , T4[FT4] ^a , triglycerides, serum amylase
Coagulation	PT-INR, and aPTT
Urinalysis	Protein, glucose, blood, microscopy assessments (if indicated), and specific gravity

ALP = alkaline phosphatase; ALT = alanine aminotransferase; AST = aspartate aminotransferase; BUN = blood urea nitrogen; LDH = lactate dehydrogenase; FSH = follicle-stimulating hormone; PT-INR = prothrombin time–international normalized ratio; T3 = triiodothyronine; FT3 = free triiodothyronine; T4 = thyroxine; FT4 = free thyroxine; TBL = total bilirubin; TSH = thyroid stimulating hormone

^a Thyroid function tests (ie, T3[FT3], T4[FT4], and TSH) will be performed as described in the Schedule of Events ([Table 6.1](#), [Table 6.2](#), and [Table 6.3](#)). More frequent examinations may be performed at the discretion of the Investigator and if indicated.

All clinical laboratory values must be assessed by the Investigator as to clinical significance and used to direct appropriate clinical management measures. All abnormal clinical laboratory values considered clinically significant by the Investigator should be recorded on the AE page of the eCRF. If the abnormal laboratory value constitutes an SAE, eCRF should be submitted and other relevant procedures must be followed (see [Section 9.5](#)). Abnormal clinical laboratory values (NCI-CTCAE Grade 3 or 4) occurring during the clinical study will be followed until repeat test results return to normal (or baseline), stabilize, or are no longer clinically significant.

9.9. Vital Signs

Vital sign measurements will include systolic and diastolic blood pressure and HR, respiratory rate, and body temperature. Additionally, pulse oximetry (SpO₂) will be performed as outlined in the Schedule of Events ([Table 6.1](#), [Table 6.2](#), and [Table 6.3](#)).

Blood pressure and HR will be measured in the resting state.

This procedure should not be conducted during the supine position for ECG measurement.

9.10. Electrocardiograms

9.10.1. Safety ECGs

The corrected QT intervals using Fridericia's formula will be used for clinical assessments and should be calculated as follows:

$$QTcF = \frac{QT}{\sqrt[3]{RR}}$$

Electrocardiograms will be performed in triplicate at baseline during Screening and evaluated by a central laboratory. Triplicate ECGs (approximately 1 minute apart) will be obtained after the subject has rested supine for at least 10 minutes. The mean QTcF of the triplicate set of ECGs will be used to determine eligibility.

12-lead ECGs will be performed at specified time points as described in the Schedule of Events ([Table 6.1](#), [Table 6.2](#), and [Table 6.3](#)). At each time point, the subject will be resting in a supine position for at least 10 minutes prior and 5 minutes after the specified times. When vital sign assessments, Safety ECGs, Endpoint ECGs, and blood sampling coincide, procedures should be carried out in said order.

Safety ECGs should be printed for each specified time point and evaluated by the Investigator on-site. Safety ECGs will also be submitted to the central laboratory. Other unscheduled ECGs may be performed as clinically indicated.

Standard ECG parameters will be measured, including RR, PR, QT intervals, and QRS duration. Please refer to the Investigator Site Manual for additional information on the collection of ECGs.

If a subject experiences QTc prolongation of Grade 4 (torsades de pointes or polymorphic ventricular tachycardia or signs/symptoms of serious arrhythmia), then the subject should be discontinued from study treatment.

9.11. Physical Examinations

Physical examinations will include evaluation of the following body systems/organs: general appearance; dermatological; head and eyes; ears, nose, mouth, and throat; pulmonary; cardiovascular; abdominal; genitourinary (optional); lymphatic; musculoskeletal/extremities; and neurological.

9.12. Other Examinations

Left Ventricular Ejection Fraction (LVEF):

- LVEF will be measured by either ECHO or MUGA, as described in the Schedule of Events ([Table 6.1](#), [Table 6.2](#), and [Table 6.3](#)). All ECHO/MUGA assessments must be evaluated by the Investigator or delegate. The same modality (ECHO or MUGA) should be used for the subject throughout the study.
- Refer to Section [17.3](#) for NYHA Functional Capacity and Objective Assessment.

Ophthalmologic Assessments:

- Ophthalmologic assessments will include visual acuity testing, slit lamp examination, fundoscopy, and tonometry as described in the Schedule of Events ([Table 6.1](#), [Table 6.2](#), and [Table 6.3](#)). All ophthalmologic assessments

must be evaluated by the Investigator or delegate. More frequent examinations may be performed at the discretion of the Investigator and if indicated. A 30-day follow-up assessment is required if an on treatment assessment was abnormal at the time of discontinuation of study therapy, to confirm reversibility of the abnormality.

Pulmonary Assessments:

- SpO₂, will be performed as described in the Schedule of Events ([Table 6.1](#), [Table 6.2](#), and [Table 6.3](#)). Additional testing to investigate pulmonary disorders may be performed, eg, chest radiograph, functional/blood-gas examination, pulmonary function testing, or serological examinations, at the Investigator's discretion as described in [Table 5.1](#). An ILD Adjudication Committee (AC) will be set up for this study. Additional details regarding the ILD AC are available in Section [11.6.6](#).

Neurologic Assessments:

- In a subject who develops new or progressive neurologic symptoms, such as peripheral neuropathy NCI-CTCAE Grade 3 to 4, delay dose and subject should be monitor at least twice a week until resolved to NCI-CTCAE \leq Grade 1. Unscheduled imaging of the brain or spinal cord may also be conducted to evaluate subjects with neurologic symptoms.

Thyroid Assessments:

- Hypothyroidism has been associated with several TKIs (eg, sunitinib and sorafenib), with increases in thyroid stimulating hormone (TSH) reported.⁴¹ Although an association with gefitinib has yet to be established, thyroid function tests (ie, T₃[FT₃], T₄[FT₄], and TSH) will be performed as described in the Schedule of Events ([Table 6.1](#), [Table 6.2](#), and [Table 6.3](#)). More frequent examinations may be performed at the discretion of the Investigator and if indicated.

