5.4.1. Dose Interruptions

During the DLT evaluation period, the administration of study drugs may be interrupted due to DLTs for up to 21 days according to the rules listed in [Table 5.1](#) below. When a DLT triggered interruption is required, both DS-1205c and gefitinib should be held. If a subject requires a dosing delay longer than 21 days, the subject will be withdrawn from the study.

For non-DLT TEAEs Grade 3 and above, study medications will be withheld for up to 3 weeks until improvement of the TEAE to Grade 2 or below. Study medications may be resumed after discussion and agreement between the Investigator and Sponsor. If the dosing interruption exceeds 21 days, the subject will be withdrawn from the study.

Table 5.1: Dose Interruption and Dose Resumption Criteria

	Worst toxicity NCI-CTCAE v5.0 Grade (unless otherwise specified) by Definition	Schedule modification for DS-1205c and gefitinib
General disorders and administration site conditions		
Fatigue/ Generalized muscle weakness	Grade 3 (Fatigue not relieved by rest, limiting self care ADL)	Delay study medications until resolved to \leq Grade 2, then: 
 • If resolved in \leq 7 days, resume study medications. • If resolved in $>$ 7 days and \leq 21 days, study medications may be resumed after discussion and agreement between the Investigator and Sponsor. • If not resolved in $>$ 21 days, discontinue subject from treatment.
Blood and lymphatic system disorders		
Neutrophil count decreased	Grade 3 ($< 1000-500/\text{mm}^3$; $< 1.0 - 0.5 \times 10^9/\text{L}$) Grade 4 ($< 500/\text{mm}^3$; $< 0.5 \times 10^9/\text{L}$)	Delay study medications until resolved to \leq Grade 2, then: 
 • If resolved in \leq 7 days, resume study medications. • If resolved in $>$ 7 days and \leq 21 days, study medications may be resumed after discussion and agreement between the Investigator and Sponsor. • If not resolved in $>$ 21 days, discontinue subject from treatment.
Febrile neutropenia	Grade 3 ($\text{ANC} < 1000/\text{mm}^3$, with a single temperature $> 38.3^\circ\text{C}$ or a sustained temperature of $\geq 38^\circ\text{C}$ for more than one hour) Grade 4 (Life-threatening consequences; urgent intervention indicated)	Delay study medications until neutrophil count decreased resolved to \leq Grade 2. Study medications may be resumed after discussion and agreement between the Investigator and Sponsor.

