Nervous system disorders	Grade 3 (Severe or medically significant but not immediately life-threatening; hospitalization or prolongation of existing hospitalization indicated; limiting self care ADL) Grade 4 (Life-threatening consequences; urgent intervention indicated)	Delay study medications and monitor at least twice a week until resolved to \leq Grade 2, then: 
 • If resolved in \leq 7 days, resume study medications. • If resolved in $>$ 7 days and \leq 21 days, study medications may be resumed after discussion and agreement between the Investigator and Sponsor. • If not resolved in $>$ 21 days, discontinue subject from treatment. Unscheduled imaging of the brain or spinal cord may also be conducted to evaluate subjects.

Table 5.1: Dose Interruption and Dose Resumption Criteria (Continued)

	Worst toxicity NCI-CTCAE v5.0 Grade (unless otherwise specified) by Definition	Schedule modification for DS-1205c and gefitinib
Eye disorders	Grade 3 (Severe or medically significant but not immediately sight-threatening; decrease in visual acuity [best corrected visual acuity worse than 20/40 or more than 3 lines of decreased vision from known baseline, up to 20/200])	
Delay dose until resolved to \leq Grade 2, then:
 
 • If resolved in \leq 7 days, resume study medications. • If resolved in $>$ 7 days and \leq 21 days, study medications may be resumed after discussion and agreement between the Investigator and Sponsor. • If not resolved in $>$ 21 days, discontinue subject from treatment. 
Ophthalmologist consult as necessary.

	Grade 4 (Sight-threatening consequences; urgent intervention indicated; best corrected visual acuity of 20/200 or worse in the affected eye)	
Discontinue subject from study treatment.
 
Ophthalmologist consult as necessary.

	Corneal ulceration, any Grade	
Discontinue subject from study treatment.
 
Ophthalmologist consult as necessary.

Renal and urinary disorders		

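### After a Grade 3–4 neurologic event, Table 5.1 ends the dose hold and monitoring at Grade 2 or below and Section 9.12 at Grade 1 or below, and no text says which governs

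*Combined protocol and SAP*

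**What the plan says.** **Table 5.1, Nervous system disorders, Grade 3 and Grade 4** (Section 5.4.1): "Delay study medications and monitor at least twice a week until resolved to \leq Grade 2, then". Three branches follow. If this took at most 7 days, the instruction is "7 days, resume study medications". If it took more than 7 and up to 21 days, resumption is possible once Investigator and Sponsor agree. Beyond that, the instruction is "21 days, discontinue subject from treatment".

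**Section 9.12, Neurologic Assessments**: "In a subject who develops new or progressive neurologic symptoms, such as peripheral neuropathy NCI-CTCAE Grade 3 to 4", the instruction is "delay dose and subject should be monitor at least twice a week until resolved to NCI-CTCAE" Grade 1 or below. Like the table row, the paragraph then allows unscheduled imaging of the brain or spinal cord. It contains no time limit, no resumption rule and no reference to Table 5.1. The pulmonary paragraph in the same section does refer to that table.

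**Section 5.4.1, general text**: for TEAEs of Grade 3 and above that are not DLTs, the hold lasts up to 3 weeks until Grade 2 or below, and resumption requires Investigator–Sponsor agreement. It adds: "If the dosing interruption exceeds 21 days, the subject will be withdrawn from the study". A 21-day withdrawal limit also applies to holds triggered by a DLT.

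**Routing.** Section 5.4 points to Table 5.1 for schedule changes after the DLT evaluation period, and Section 5.4.1 points to it for DLT-triggered interruptions. The note under Table 5.1 allows documented case-by-case exceptions.

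**The concern.** The two passages share the trigger grades, the action, the monitoring frequency and the imaging sentence. They differ in the recovery grade, which decides when a subject may be dosed again. Section 15.5 bars deviations except to remove an immediate hazard. On its natural reading, a site that resumes at Grade 2 therefore complies with Table 5.1 and departs from Section 9.12.

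What is at stake is re-exposure after a severe or life-threatening neurologic event. The drug has no human safety data at the time of writing (Sections 1.1.3 and 1.4.1), about 20 sites are planned (synopsis), and there is no data monitoring committee (Section 11.8). Exposure and reasons for ending treatment are summarized (Section 11.3), and tumor assessments stop at permanent treatment discontinuation (Section 7.1.1). The choice of passage can therefore also change what is recorded for a subject.

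**Working it through.** The documents give no figure to reproduce. The check traces one subject's recovery through both rules.

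Let T2 be the first day at Grade 2 or below and T1 the first day at Grade 1 or below, counted from the start of the hold, with no later worsening. Then T1 ≥ T2.

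- Table 5.1: the hold ends at T2, with branches at 7 and 21 days.
- Section 9.12: the hold ends at T1. It has no limit of its own, so the 21-day limit has to come from Section 5.4.1 or Table 5.1.
- Difference in hold length where both holds end within the limit: T1 − T2.

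| Recovery path | Table 5.1 | Section 9.12 with the 21-day limit | Difference |
|---|---|---|---|
| (a) T2 ≤ 7, T1 > 21 | Row allows resumption at T2 | Hold passes day 21: discontinued or withdrawn | Opposite outcomes |
| (b) T2 ≤ 7, T1 from day 8 to day 21 | Row allows resumption at T2 | Held until T1 | Longer hold, no withdrawal |
| (c) T1 = T2 (straight to Grade 1 or below) | Hold ends at T2 | Hold ends on the same day | None |
| (d) T2 > 21 | Discontinued | Discontinued or withdrawn | None in dosing |

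Illustration, with T2 assumed to be day 5. If T1 is day 21, Section 9.12 adds 21 − 5 = 16 days to the hold and the subject stays in the study. If the subject is still at Grade 2 after day 21, path (a) applies.

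If T2 falls between day 8 and day 21 and T1 is after day 21, the split has the same form, but resumption under Table 5.1 then depends on Sponsor agreement.

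**Sponsor agreement.** In paths (a) and (b) the table row does not ask for agreement before resumption. Section 5.4.1 asks for it for every non-DLT TEAE of Grade 3 and above, with no exemption for resolution within 7 days. The two texts conflict on this step as well.

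**Reading *until* in Section 9.12 as governing only the monitoring.** The end points for monitoring still differ (Grade 1 against Grade 2), and Section 9.12 then orders a delay without saying when it ends.

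**The case against.** The strongest reply is that the documents already identify the operative dosing table. Section 5.4 and Section 5.4.1 between them send dosing to Table 5.1 both during and after the DLT period. The general rule in Section 5.4.1 is also Grade 2 or below, and Section 9.12 is about examinations. If *until* governs only the monitoring, a site could dose by Table 5.1, monitor to Grade 1, and satisfy both passages. This has force: a careful reader would probably go to Table 5.1 first. It does not remove the conflict, because no text makes Section 9.12 subordinate, its sentence opens with a dose delay, and the exception note does not say which grade governs.

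Some stronger inferences are tempting, and the documents do not support them:

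- *Every such subject is either re-dosed within days or withdrawn at day 21.* Of the four paths in the table, only path (a) splits this way. The limit is also not in Section 9.12, and a site that takes it from Section 5.4.1 or Table 5.1 will see Grade 2 there.
- *Sites would resume within 7 days without the Sponsor.* The table row permits this, but Section 5.4.1 does not for non-DLT TEAEs of Grade 3 and above. Under Section 3.2.1.4, DLTs are reported to the Sponsor in real time.
- *The rate of discontinuation for adverse events moves by 5.6 percentage points.* That is 1/18, the weight of any one subject among 18. The organs listed with histopathological findings in Sections 1.1.2.4 and 1.4.1 do not include the nervous system, and no frequency for such events is given.
- *DLT counts, PFS or DOR are shown to change.* DLT status for a Grade 3–4 event does not turn on this recovery grade, and no effect on PFS or DOR can be quantified from the documents.

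**Conclusion.** The contradiction stands. Two instructions for the same Grade 3–4 neurologic event name different recovery grades, and nothing in the documents settles which applies. The hold differs by T1 − T2 for a subject who passes through Grade 2 and reaches Grade 1 within the limit. The outcome reverses for a subject who reaches Grade 2 within 7 days and remains there past day 21. That reversal assumes that Section 9.12 governs the dose delay and is read together with the 21-day limit found elsewhere. Such a plateau is possible under the plan, since inclusion criterion 6 admits subjects with existing TKI-related toxicity below Grade 3, but how often it would occur is unknown. The case for correction rests on incompatible instructions for re-exposure, not on an estimated effect on any endpoint. No position is taken on which grade is right.

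**What to change.** Reconcile Table 5.1 (Nervous system disorders), the general text of Section 5.4.1 and Section 9.12:

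1. State one recovery criterion in the Table 5.1 row for both the dose hold and the twice-weekly monitoring. If the two are meant to end at different grades, say so explicitly. The sponsor's clinical team chooses.
2. Replace the threshold in the neurologic paragraph of Section 9.12 with a cross-reference to that row.
3. Make the row and Section 5.4.1 agree on whether Sponsor agreement is needed when resolution takes 7 days or less.
4. While editing, align the consequence past 21 days: Table 5.1 discontinues treatment, whereas Section 5.4.1 withdraws the subject from the study.

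The cost is a short text amendment, with no added subjects. The corrections themselves require no added visits.

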10. OTHER ASSESSMENTS

Not applicable.

11. STATISTICAL METHODS

11.1. General Statistical Considerations

Descriptive statistics will be provided for selected demographic, safety, PK, and biomarker data from both Dose Escalation and Dose Expansion by dose level within each part and visit as appropriate. Descriptive statistics for continuous data will include means, medians, standard deviations, and minimum and maximum, while categorical data will be summarized using frequency counts and percentages. Graphical summaries of the data may be presented.

Assessments of change from baseline to post-treatment or the ratio of post-treatment to baseline will include only those subjects with both baseline and post-treatment measurements. The last non-missing value of a variable taken before the first dose of study drug will be used as the baseline value, unless otherwise specified. Time-matched baseline will be derived from Cycle 0, Day -1 measurements for all ECG.

Safety analyses will be performed based on the safety analysis sets. Analysis of PK parameters will be based on the PK analysis sets, and biomarker analyses will be based on the PD biomarker analysis sets.

Efficacy endpoints will be analyzed based on the Full Analysis Set (FAS). Data from Dose Escalation will be summarized by dose level within each part and overall.

A detailed statistical analysis plan (SAP) describing the methodology to be used in the final analysis will be prepared and finalized before database lock. Statistical methods described within may be changed based on advances in research.

11.2. Analysis Sets

- Enrolled Analysis Set will include all subjects who sign the ICF of the study.
- FAS will include all subjects in the Enrolled Analysis Set who received at least one dose of DS-1205c and who had baseline and post-treatment evaluable tumor assessments.
- DLT-Evaluable Set will include subjects enrolled in Dose Escalation who had at least one DLT during the 7 days of Cycle 0 or the 21 days of Cycle 1, or did not have a DLT but received at least 75% of the doses in the 21 days of Cycle 1.
- Safety Analysis Set will include all subjects in the Enrolled Analysis Set, who received at least one dose of DS-1205c. Four groups of subjects will be identified within the Safety Analysis Set: (1) subjects in Dose Escalation, (2) subjects in Dose Expansion, (3) subjects treated at the dose level of RDE, and (4) all treated subjects in the study.
- PK Analysis Set will include all subjects in the Enrolled Analysis Set who received any amount of the study drugs and have sufficient plasma concentration data to characterize PK of DS-1205a or gefitinib.

- Concentration-QTc Analysis Set will include all subjects who are in the Safety Analysis Set with at least one pair of postdose plasma concentration data and QTc data from the same timepoint. The concentration-QTc Analysis Set will be used for the concentration-QTc analysis.
- Biomarker Analysis Set will include all subjects in the Enrolled Analysis Set who received any amount of study drugs and who had the baseline tissue biopsy assessment and, where applicable, at least 1 post-treatment blood sample assessment for biomarkers.

